Rationale: We need to assure that the new method produces rates of appearance (Ra) of hepatic glucose release and adipocyte free fatty acid release that are within range of those calculated following the hyperinsulinemic euglycemic clamp which is currently accepted as the gold standard method to assess IR using only an IV approach.

Methods: An additional 9 subjects will be enrolled and studied with the OG model. Data from the raw suppressed glucose and glycerol Ra, insulin concentration required for 50 percent of peak suppression and percent suppression of basal Ra will be compared between OG subjects and a matched cohort of girls whom have already undergone hyperinsulinemic euglycemic clamps with identical glucose and glycerol tracer infusion rates.

Aim 1C: Optimize timing of data collection with ^{31}P -MRS in the liver related to a glucose load.

Rationale: Studies in adults have shown that glycogen synthesis increases by 1 hour post glucose load. A preliminary step to glycogen synthesis or hepatic glucose utilization is passage of glucose

through glucose-6-phosphate (G-6-P). Increased concentrations of G-6-P should be detectable 45 min after a glucose load.

Methods: We will collect ^{31}P data from the liver when subjects are fasted, and 45 min following an 75 gram oral glucose load.

Specific Aim 2: Test the impact of oral glucose on hepatic and adipocyte insulin sensitivity in PCOS, and the effect of common medical therapies metformin and oral contraceptives on hepatic and adipose insulin sensitivity

Rationale: Insulin sensitivity is traditionally assessed with IV only methods. However these do not allow for the contributions of gut hormones, and are non-physiologic. We have previously found significant decreases in hepatic and adipose insulin sensitivity in girls with PCOS and need to determine if this is also seen following a glucose load, as this would be reflective of daily life. Further, the effect of current therapies has not been assessed with this method.

Methods: Perform OGTT's with tracers in obese girls with and without PCOS, and girls with PCOS who have been taking oral contraceptives or metformin.

Specific Aim 3: Determine the role of hepatic and adipose IR in the rate of hepatic de novo lipogenesis (HDNL) and the effect of common medical therapies metformin, oral contraceptives and GLP-1 receptor agonists on HDNL

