Obese adolescents are at risk of T2D and its complications, reduced exercise capacity, increased liver and visceral fat, muscle dysfunction and cardiovascular dysfunction therefore the tests performed screening for each of these problems provide useful information to these subjects. Likewise, sedentary subjects of any weight are at increased risk of reduced bone mineral density (BMD), T2D, reduced exercise capacity, increased liver and visceral fat, muscle dysfunction and cardiovascular dysfunction. Therefore, all of the subjects may benefit from the results of DEXA, glucose testing and exercise prescription and dietary counseling.

C. Study Design and Research Methods

Study Calendar	Visit 1 – Screen	Visit 2 –MRI	Visit 3 – Overnight
Consenting and Eligibility Assessment	X		
History & Physical	X		
Intravenous Blood Draw	X		X
Finger Stick Blood Draw		X	
Urine Pregnancy Test			X
Accelerometer Teaching	X		
Gut Bacteria Collection			X
Questionnaires- SEARCH Food frequency, Activity 3DPAR, Strengths and Difficulties, a sleep diary, and Sleep assessments			X
Sleep Study with salivary melatonin collection (pending scheduling)			X
WatchPAT sleep study			X
DEXA Scan			X
Glucose, Glycerol and Acetate Tracers			X
Study Drug (Byetta) GLP-1 Injection			X
EndoPat and Dynapulse		X	
MRI of abdomen and liver, P MRS of Liver		X	
Metabolic Cart			X
Total Time of visit (approximately)	3 Hours	2 Hours	24 Hours
Location of Visit	CHCO CTRC Outpatient	UCD Outpatient Brain Imaging Center	CHCO Inpatient Hospital

The study consists of 3 visits - 2 outpatient visits and one overnight inpatient visit. Inpatient visit will last approximately 24 hours, outpatient screening visit approximately 3 hours, outpatient MRI visit approximately 2 hours. The 3 visits would be completed within 4 months time.

Overall enrollment procedure plan per group

Test Group	Screening	MRI/MRS	Overnight stay	Glucose and Glycerol tracers	DEXA	Overnight acetate tracer	GLP-1 Injection (Byetta)
PCOS	40-50	50	50	50	50	30	10
PCOS w/ Metformin	10-13	10	10	10	10	5	0
PCOS w/ OCP's	10-12	10	10	10	10	5	0
Obese	20-30	20	20	20	20	10	0
Total	Up to 105	90	90	90	90	50	10

VISIT 1 (SCREEN VISIT)

Pediatric CTRC Outpatient unit: Participants will begin with a medical screening and physical exam. During this visit, patients will review and complete consent documents, have demographics

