The stable isotope method to be utilized is an OGTT with IV glucose and glycerol stable isotope tracers in all subjects, and acetate tracers in select subjects, based on power analysis and cost. For the glucose and glycerol tracers, we will utilize the tracer doses as in our previous hyperinsulinemic clamp studies, as these rates successfully detected basal and stimulated glucose and glycerol Ra. Whole-body lipolysis will be measured under basal conditions and during the OGTT (75 grams glucose + 25 grams fructose + ¹C₁₃ tracer), using a primed (1.6 μ mol/kg), constant (0.11 μ mol/kg/min) infusion of ²H₅glycerol⁴⁷. Hepatic IR will be measured under basal conditions and during the OGTT, using a primed (4.5 mg/kg), constant (0.03 mg/kg/min) infusion of 6,6-²H₂glucose⁴⁸. Blood sampling will continue for 6 hours post-OG to allow return to baseline, based on our pilot data shown in Figure 2 that 2 hours is inadequate. Blood for tracer analysis and glucose and insulin concentrations will be drawn at baseline, every 10 min during the last 40 min of the basal period, and every 15 min post OG load.

The rate of the acetate tracer will be 2 μ mol/kg/min with no prime, based on previous studies⁴⁹. The oral challenge study design is shown in Figure 4. Hepatic De Novo lipogenesis will be measured in the fasting state, and in the fed state following the glucose load, by analyzing the incorporation of the C₁₃ tracer into hepatically secreted lipids such as 16 and 18 carbon long chain

Figure 4: Proposed Oral Glucose Challenge

fatty acids in VLDL⁴⁹. Blood will be drawn at baseline and for the last 4 hours of the basal state and the postprandial state.

A total of 40 girls will receive the overnight acetate infusion. This total will be broken down into 20 un-treated PCOS patients (10 without Byetta and 10 with Byetta), 10 obese control patients and 10 from PCOS patients treated with Metformin or OCP (5 from each group). Analysis of $^2\text{H}_5\text{glycerol}$, 6,6- $^2\text{H}_2$ and long chain fatty acid incorporation of $^2\text{C}_{13}$ Acetate, will be performed by our collaborator [name], using a modification of the negative ion chemical ionization gas chromatography mass spectrometry as in our previous studies^{49,50}.

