The protocol as described includes the entire subject set, which allow for comparisons between obese girls with and without PCOS. OGTT with tracers will be conducted in all subjects, and overnight assessment of HDNL in 20 subjects (10 with PCOS and 10 without). However, data from the first 6-12 subjects (both PCOS and non-PCOS) will be immediately evaluated to see if any changes are needed in terms of protocol details. The specific points that are to be evaluated are listed below:

1) OGTT with glucose and glycerol tracers

- a. Purpose: Develop an oral stimulus model to assess hepatic and adipose insulin sensitivity.
- i. Question 1. Is 4 hours post oral load long enough to model hepatic and adipose insulin sensitivity?
 1. Rationale: Our preliminary data from OGTT's in obese girls indicates that subjects' insulin and glucose concentrations have not returned to baseline by 2 hours. Data from adults showed that all non-diabetic adults were back to baseline by 3.5 hours.
 2. Measurement. Serum glucose and insulin will be measured post-glucose load for 4 hours in the first 6 subjects. If 4 hours post glucose values are within 10 mg/dL for glucose and 10 IU/mL for insulin relative to baseline values, 4 hours will be considered sufficient.
- ii. We are revising the protocol to 6 hours based on our results from our first several subjects. Question 2: Are glucose and glycerol Ra during the OGTT similar to those obtained with a hyper-insulinemic euglycemic clamp.
 1. Rational: Peak insulin concentrations are similar between an OGTT and a clamp, thus Ra rates should also be similar. Comparisons in adults of the glucose Ra from clamps and an oral meal challenge were similar.
 2. Measurement: The peak suppressed glucose and glycerol Ra for the first 12 subjects will be compared to peak suppressed Ra values calculated from data from 70 girls during hyper-insulinemic euglycemic clamps.
 3. Revision plan if model not correct: None. Findings of either similar or different glucose and glycerol Ra are valuable information.

2) Measurement of Hepatic De Novo Lipogenesis (HDNL)

- a. Purpose: Optimize a model to asses HDNL with minimal blood draws, minimal time of tracer intervention and no interference with measures of glucose and glycerol
 - Ra

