If a subject experiences any of the following, the subject will be withdrawn from the study.

1. Inability to complete study procedures
2. Abnormal screening labs (LFT's >4 times elevate, HbA1C>6.4%, Hg <9 mg/dL)
3. Subject becomes pregnant during study

D. Protocol Stopping Criteria

If one or more subjects experience any of the SAE's listed above, the PI will consult with the mentor prior to continuing study visits with subjects. The mentor and RSA will consult about the significance of the SAE's and make a recommendation to the PI.

VII. Data Analysis Plan:

Statistical Plan for Method Development: The previously described tracer protocol and mathematical modeling with any refinements will be performed in an additional 9 subjects. Outcome measures (raw suppressed glucose and glycerol Ra, insulin concentration required for 50 percent of peak suppression and percent suppression of basal Ra) will be compared between the OG subjects and a matched cohort of girls who have undergone hyperinsulinemic euglycemic clamps with identical glucose and glycerol tracer infusion rates. Subjects in the two groups will be matched on PCOS diagnosis, race, percent body fat, percent liver fat, and time post-menarche. An equivalence design will be used to compare the outcomes in the two groups and to demonstrate whether there are clinically significant differences in outcomes from the OG model and the hyperinsulinemic clamp. For purposes of sample size calculation, we used estimates from the investigator's pilot study. Using an equivalence limit of one standard deviation for each outcome measure (SD=50 units for glycerol IC50 and SD=39 units for glucose IC50) and a correlation of 0.2 between outcomes on matched subjects, 15 matched pairs gives 80% power to demonstrate equivalence. 70 girls have completed the hyperinsulinemic euglycemic clamps, so adequate matching will be possible.

Overall Project Statistical Plan:

Power calculation: The primary outcome is hepatic IR measured as IC₅₀ glucose Ra. Using our preliminary data, a two-tailed t-test and an alpha of 0.05, completing 13 controls and 32 PCOS provides 86% power to detect a difference of 35 IU/L in the insulin concentration.

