Differences between the two primary groups (PCOS, controls) will be assessed with a t test or for non-normally distributed data a non-parametric test such as Mann-Whitney U. Secondary outcomes include a Pearson correlation test of potentially related variables followed by targeted multiple regression to assess the relationship between hepatic IR or hepatic fat and adipose IR, hepatic gluconeogenesis, VAT, carbohydrate oxidation, androgens, metformin or OPC use and presence of OSA. As an exploratory analysis, the four groups will also be compared using an ANOVA. We recognized that we may not be powered for these analyses, but the data will be used as hypothesis generating for future studies.

The rate of hepatic De Novo lipogenesis is a secondary outcome. Based on our preliminary data that plasma markers of hepatic De Novo lipogenesis are 40% greater in those with fatty liver disease and the use of a high carbohydrate and fructose drink to increase the differences between groups, 10 subjects in each group will be needed to detect a difference in hepatic De Novo lipogenesis^{21,49,52}. The rate of hepatic De Novo lipogenesis will be correlated with measures of hepatic and adipose IR and MRI measures of NAFLD.

Non-Isotope OGTT calculations: The Matsuda model of IR will be used, and B-cell function [insulinogenic index ($\Delta I30/\Delta G30$) and ($\Delta C30/\Delta G30$) and disposition index ($1/IFasting \times \Delta I30/\Delta G30$) and ($1/CFasting \times \Delta C30/\Delta G30$) will be calculated^{40,53-55}.

Proposed Mathematical Model of Glucose and Glycerol Dynamics: The differential equations-based isotope labeled oral glucose minimal model (OMM*)⁵⁶ will be adapted to describe glucose and glycerol dynamics present in the collected data. In OMM*, the oral glucose minimal model (OMM) is modified to account for labeled glucose oral data obtained with the inclusion of a stable isotope tracer. This refinement allows an estimate of insulin sensitivity which is unique in that it accounts for both stimulation of adipose and muscle glucose uptake and inhibition of hepatic glucose release. In OMM*, glucose concentration G and insulin action on glucose disposal X are governed by the following equations:

$$\begin{aligned}\frac{dG}{dt} &= -[S_G^* + X^*] \cdot G + \frac{R_a(\alpha, t)}{V^*} \\ \frac{dX^*}{dt} &= -p_2^* \cdot X^* + p_3^* \cdot [I - I_b]\end{aligned}$$

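### HDNL is said to need 10 girls per group, but the metformin and OCP groups get 5 acetate infusions each, and the number of girls receiving acetate is given as 20, 40 and 50

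*Combined protocol and SAP*

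**What the plan says.** **Required size.** Section VII, Overall Project Statistical Plan, makes HDNL a secondary outcome and says "10 subjects in each group will be needed to detect a difference in hepatic De Novo lipogenesis". The stated basis is that "plasma markers of hepatic De Novo lipogenesis are 40% greater in those with fatty liver disease", together with a drink chosen to widen group differences. No SD, power or alpha is given for HDNL.

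**Question asked.** Specific Aim 3 (section I) covers the role of insulin resistance in HDNL and also "the effect of common medical therapies metformin, oral contraceptives and GLP-1 receptor agonists on HDNL".

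**Allocation.** Three places in the current text give numbers:

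| Place | Untreated PCOS | Metformin | OCP | Controls | Total |
|---|---|---|---|---|---|
| III.C, table "Overall enrollment procedure plan per group" | 30 | 5 | 5 | 10 | 50 |
| III.C, Visit 3, Details of Stable Isotope Tracer studies | 20 (10 with exenatide, 10 without) | 5 | 5 | 10 | 40 |
| IV, Limitation of Method Development | 10 (PCOS, treatment not specified) | not named | not named | 10 | 20 |

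The Visit 3 text reads "A total of 40 girls will receive the overnight acetate infusion" and assigns "10 from PCOS patients treated with Metformin or OCP (5 from each group"). Section IV has "overnight assessment of HDNL in 20 subjects (10 with PCOS and 10 without"). According to the exenatide paragraph under Visit 3, the 10 exenatide girls are untreated PCOS girls who also receive acetate. They therefore sit inside the 30 or the 20.

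**Caveat.** The paragraph before the HDNL sizing calls the four-group ANOVA exploratory, concedes that power may be lacking, and describes the data as hypothesis generating. The HDNL paragraph has no such statement.

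**The concern.** The plan sets a size for HDNL and then gives two of the three therapy groups named in Aim 3 half of it. The table and the Visit 3 text agree on 5 and 5, so a slip in one place does not explain it. Only the exenatide subset reaches 10.

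As written, nothing in the HDNL paragraph tells the analyst or reader that these contrasts fall short of the stated size. A non-significant result from five girls could then be reported as absence of a drug effect on HDNL.

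The conflicting totals are a separate defect. They leave open how many adolescents receive the overnight tracer infusion, and how many untreated girls serve as comparators for the treated groups.

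**Working it through.** **1. Totals**
- Table: 30 + 5 + 5 + 10 = 50.
- Visit 3 text: 20 + 10 + 10 = 40, where one of the tens is 5 metformin + 5 OCP.
- Section IV: 10 + 10 = 20.

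The gap between 50 and 40 lies wholly in untreated PCOS (30 v 20). The treated groups have 5 each under either. Untreated girls without exenatide number 30 − 10 = 20 under the table and 20 − 10 = 10 under the text.

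**2. Can the 10 per group be reproduced?** Not from the documents, because SD, power and alpha are missing. The only HDNL marker with a spread is FFA n7 in Table 1: 29±13 in controls and 45±15 in PCOS. Read ± as SD (the table does not say), and assume two-sided alpha 0.05 and 80% power.
- Pooled SD = √((13² + 15²)/2) = 14.04.
- n per group = 2(1.96 + 0.842)²/d² (normal approximation).
- Observed difference: d = (45 − 29)/14.04 = 1.14, giving 13 per group.
- A 40% difference: d = 0.40 × 29/14.04 = 11.6/14.04 = 0.83, giving 23 per group.

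If ± were a standard error, the requirement would be in the hundreds (361 and 687). FFA n7 in PCOS v control is also only a proxy for the fatty-liver contrast on which the plan bases its 10. The figures below therefore take the 10 at face value and ask what halving one arm does.

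**3. Power relative to the plan's own standard.** Assumption: 10 v 10 means 80% power with "a two-tailed t-test and an alpha of 0.05". The plan states that test and alpha for the primary outcome only. For a two-sample t-test,

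power = P(|T| > t₀.₉₇₅,df), where T is noncentral t with df = n₁ + n₂ − 2 and noncentrality d√(n₁n₂/(n₁ + n₂)).

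Setting power to 0.80 at 10 v 10 gives d = 1.32 (1.325 to three decimals). With that d held fixed:

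| Contrast | Noncentrality | Critical t | Power | d detectable at 80% |
|---|---|---|---|---|
| 10 v 10 | 2.96 | 2.101 | 80% | 1.32 |
| 5 v 10 (text, 40) | 2.42 | 2.160 | 61% | 1.66 |
| 5 v 20 (table, 50) | 2.65 | 2.069 | 72% | 1.46 |
| 5 v 5 (metformin v OCP) | 2.09 | 2.306 | 45% | 2.02 |

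In percentage terms, a design that detects 40% at 10 v 10 detects 40 × 1.66/1.325 = 50% at 5 v 10, 44% at 5 v 20 and 61% at 5 v 5.

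**4. Sensitivity**
- If 10 v 10 means 90% power (d = 1.53), the three smaller contrasts have about 73%, 84% and 57%.
- With the Table 1 proxy at d = 1.14, power is 67% (10 v 10), 49% (5 v 10) and 59% (5 v 20). At d = 0.83 it is 42%, 29% and 35%.

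In every case the contrasts with 5 girls fall below the 10 v 10 benchmark.

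**The case against.** **The group meant may be PCOS v control.** The analysis plan opens with those two primary groups, the 10 rests on a fatty-liver difference and not on a drug effect, and section IV gives exactly 10 with PCOS and 10 without. On that reading the controls and untreated PCOS girls satisfy the requirement and the fives do not breach it. This is plausible and cannot be ruled out. But it would mean that the therapy effects on HDNL named in Aim 3 have no sample-size basis, so the text would still have to say which groups the 10 covers.

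**The plan already concedes limited power.** The only comparison of metformin and OCP users as groups in section VII is the exploratory ANOVA, and section III.E claims only a beginning in learning about the therapies. That reduces the risk of misreading. It does not remove it: the caveat precedes the HDNL paragraph, which then gives its own size without qualification.

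**A stronger reading.** A reader might infer that the metformin and OCP effects on HDNL cannot be tested at all. The documents do not support that. The contrasts can be run at lower power, and the only HDNL analysis spelled out in section VII is correlation with insulin resistance and MRI measures.

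**Pooling the treated groups.** Combining metformin and OCP users would reach 10 but would not separate the two effects. The study hypothesis expects them to move insulin resistance in opposite directions.

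**Conclusion.** The point holds as a mismatch between stated size and allocation, plus three incompatible totals. The totals and the allocation of 5 and 5 follow by addition and rest on no assumption. The metformin and OCP contrasts for HDNL are underpowered by the plan's own standard: about 61% or 72% against untreated PCOS, depending on which total is right, and 45% against each other.

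Those percentages assume that 10 v 10 corresponds to 80% power, a two-sided alpha of 0.05 and a t-test. The documents state none of these for HDNL. The direction does not depend on them, and the size shifts as shown for 90% power and for the Table 1 proxy. This concerns a secondary outcome. It does not affect the primary comparison of IC₅₀ glucose Ra.

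**What to change.** 1. Reconcile the enrollment table, the Visit 3 tracer text and section IV to one acetate total and one split by group, showing the exenatide girls as their own line.
2. In the HDNL paragraph of section VII, state that 10 per group applies only to the untreated PCOS, exenatide and control groups, and give the SD, alpha and power behind it.
3. In the same paragraph, state that the metformin and OCP contrasts for HDNL (n = 5 each) are descriptive, reported as estimates with confidence intervals, and that no conclusion of no effect will be drawn from a null result. Extend the existing power caveat explicitly to HDNL.

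The cost is wording in three sections and one table, with no added infusions or participants.

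Re-splitting the table's 50 infusions as ten in each of five groups is not recommended as the remedy. It would cut untreated PCOS girls without exenatide from 20 to 10. At d = 1.14, power for untreated PCOS v control would then fall from 81% (20 v 10) to 67% (10 v 10). It would also need acetate in all 10 girls planned for each treated group, leaving no slack.

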WatchPAT: During the hospital overnight stay, trained study staff will place the WatchPAT sleep monitor. The primary measures will be for oxygen saturation and apnea hypopnea index (AHI). Each participant will wear the watch with a one-time use finger cuff as recommended by the FDA. The watch will be placed by 8 PM, and will be removed the following morning.

The following morning, a blood sample for baseline metabolic labs will be drawn and infusion studies with the modified OGTT will be completed.

Study Drug Injections Exenatide (Byetta):

[figure not shown]
A subset of 10 untreated girls with PCOS who are receiving the overnight Acetate infusion will be administered two injections of Exenatide (Byetta) (5 mcg) during the in-patient admission for the OGTT. The first injection will be administered the night of admission at 6:30-7 PM. 30 minutes prior to the study diet containing a fixed macronutrient distribution listed below. The subject will be monitored throughout the night by nursing staff. The second injection will be administered at approximately 8 AM, 30 minutes prior to the OGTT load of 75 grams glucose. Following the second injection, study staff and CTRC nursing staff will be bedside for the remainder of the patient's inpatient admission at CHCO. Blood glucose measurements will be taken regularly for 6 hours post OGTT.

Details of Stable Isotope Tracer studies with an OGTT: After the overnight fast, subjects will consume a 75 grams glucose load with an additional 25 grams of fructose to stimulate hepatic de novo lipogenesis, and a ¹C₁₃ glucose tracer (40 mg/kg) to calculate the rate of appearance of exogenous glucose²¹.

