where S_G^* is the fractional glucose effectiveness; $R_a(\alpha, t)$ is the glucose rate of appearance; V^* is the distribution volume; p_2^* and p_3^* are rate constants; I is plasma insulin concentration; and I_b is basal plasma insulin concentration. The R_a in this equation represents a best fit (see Fitting Ra below) to R_a values computed from data (see Proposed Isotope Tracer Calculations below). This model will allow differentiation between exogenous and endogenous contributions to changes in glucose concentration. A similar model, modified to reflect the absence of an exogenous glycerol contribution from OGTT, will be used to describe glycerol dynamics. The concomitant study of glycerol has been shown to not interfere or contribute to glucose R_a .⁵⁷

Proposed Isotope Tracer Calculations: The glycerol and glucose R_a during fasting and the entire post-glucose load period will be calculated using the non-steady-state equation of Steele^{58,59}. The glucose rate of disappearance (R_d), and metabolic clearance rate (MCR) will be calculated for the same time periods^{58,59}.

$$\begin{aligned}R_a \text{ (mg} \cdot \text{kg}^{-1} \cdot \text{min}^{-1}) &= (F - V((C_1 + C_2)/2)((IE_2 - IE_1)/(t_2 - t_1))) / ((IE_2 + IE_1)/2) \\ R_d \text{ (mg} \cdot \text{kg}^{-1} \cdot \text{min}^{-1}) &= R_a - V((C_2 - C_1)/(t_2 - t_1)) \\ MCR \text{ (ml} \cdot \text{kg}^{-1} \cdot \text{min}^{-1}) &= R_d / ((C_1 + C_2)/2)\end{aligned}$$

where F represents isotope infusion rate; IE_1 and IE_2 are isotopic enrichments at sampling time points 1 (t_1) and 2 (t_2), respectively; C_1 and C_2 are metabolite concentrations at t_1 and t_2 ; and V is the estimated volume distribution (glucose is 180 ml/kg and glycerol 27 ml/kg). R_a glucose from the glucose drink ($R_{a,EXO}$) and endogenous glucose production ($R_{a,ENDO}$) will be calculated:

$$\begin{aligned}\%R_a \text{ from EXO} &= (E_P/E_D)100 \\ R_{a,EXO} &= R_a(\%R_a \text{ from EXO})/100 \\ R_{a,ENDO} &= R_a - R_{a,EXO}\end{aligned}$$

where E_D and E_P are the enrichments of the 1-¹³C-glucose in the drink and plasma, respectively. R_a , R_d and MCR will be presented with and without correction for serum insulin concentrations.

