Proposed Model of Glucose Absorption: A key advantage of OGTT over IV glucose delivery is the physiologic aspect of oral administration. When glucose is ingested, the physiologic pathway through the gastrointestinal tract contributes to the glucose rate of appearance in plasma. Although gastric emptying of liquids occurs exponentially in control subjects, there is evidence that gastric emptying may be delayed in certain populations, thereby impacting glucose absorption⁶³⁻⁶⁵. In order to assess possible abnormalities in glucose absorption in PCOS, we will relate a model that describes mechanisms of glucose transit through the gastrointestinal tract⁶⁰ to Ra data computed for PCOS subjects. The three-compartment model for glucose transit through the stomach and upper small intestine is described by the following system of differential equations:

$$\begin{aligned}\frac{dq_{sto1}}{dt} &= -k_{21}q_{sto1} + D\delta \\ \frac{dq_{sto2}}{dt} &= -k_{empt}(q_{sto})q_{sto2} + k_{21}q_{sto1} \\ \frac{dq_{gut}}{dt} &= -k_{abs}q_{gut} + k_{empt}(q_{sto})q_{sto2}\end{aligned}$$

where q_{sto1} and q_{sto2} are the amounts of glucose in the stomach (solid and liquid phase, respectively); δ is the impulse function associated with OGTT glucose delivery; D is the amount of ingested glucose; q_{gut} is the glucose mass in the intestine; k_{21} is the rate of grinding; and k_{abs} is the rate constant of intestinal absorption. The rate of gastric emptying, $k_{empt}(q_{sto})$, is a nonlinear function of the total amount of glucose in the stomach: $q_{sto}=q_{sto1}+q_{sto2}$. Then we compute $Ra(t) = f K_{abs} q_{gut}(t)$ where f is the fraction of intestinal absorption appearing in plasma. Model parameters will be determined by fitting to Ra and tracer data. Since model parameters reflect specific physiologic processes, they will provide additional insight into the mechanisms underlying abnormalities of glucose Ra in PCOS subjects.

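### The split of post-drink glucose Ra omits the term for changing plasma oral-tracer enrichment, so endogenous Ra is too high early and too low late

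*Combined protocol and SAP*

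**What the plan says.** In Section VII, Proposed Isotope Tracer Calculations, glucose and glycerol Ra "during fasting and the entire post-glucose load period will be calculated using the non-steady-state equation of Steele". That equation contains the change in infused-tracer enrichment between consecutive samples. Post-drink glucose Ra is then divided into two sources. The drink's percentage is given as "from EXO} &= (E_P/E_D)100", where E_P and E_D are the 1-13C-glucose enrichments of plasma and drink. Ra,EXO is Ra times that percentage, and Ra,ENDO is Ra minus Ra,EXO. No term for a change in E_P appears.

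The oral tracer is given once, in the drink, "to calculate the rate of appearance of exogenous glucose" (Section III.C, Visit 3). Blood is drawn for 6 hours, "and every 15 min post OG load". The same section says "Hepatic IR will be measured under basal conditions and during the OGTT". Under Overall Project Statistical Plan: "The primary outcome is hepatic IR measured as" IC50 glucose Ra.

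Two models draw on these results. The Ra in the labelled oral minimal model (OMM\*) is a best fit to "values computed from data (see Proposed Isotope Tracer Calculations below"). For the absorption model, "Model parameters will be determined by fitting to Ra and tracer data".

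**The concern.** E_P/E_D describes the composition of the plasma glucose pool. Ra,EXO is a rate of entry into that pool. The two shares agree only when the composition is not changing. Just after the drink the pool contains almost no drink glucose although drink glucose is entering fast, so the ratio assigns too little of Ra to the drink and too much to the liver. Later the pool still holds drink glucose although little is entering, and the error reverses.

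The plan corrects for changing enrichment of the infused tracer and, a few lines later, makes no such correction for the oral tracer, whose enrichment starts near zero.

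At stake is the measure of hepatic insulin resistance. An IC50 is read where endogenous Ra has fallen by half, which happens while E_P is still climbing and insulin is changing. The error depends on each subject's glucose and absorption curves, so it cannot be assumed to cancel between PCOS and control girls. In Aim 1B the comparison cohort had an IV-only clamp with no drink to subtract, so the error would sit on one side.

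**Working it through.** The plan states no numerical result for this split, so there is no figure to reproduce. The check has three parts: algebra, hand arithmetic and simulation.

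**Algebra.** Let f = E_P/E_D, so that drink glucose in plasma is V × C × f.

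1. Balance for drink glucose: d(V × C × f)/dt = Ra,EXO − Rd × f.
2. The plan's disposal equation: Rd = Ra − V × dC/dt.
3. Expand the left side of step 1 and insert step 2: V × f × dC/dt + V × C × df/dt = Ra,EXO − Ra × f + V × f × dC/dt.
4. Cancel: **Ra,EXO = Ra × f + V × C × df/dt.**

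The plan keeps only Ra × f. Because Ra,ENDO is the remainder, its error is +V × C × df/dt. The sign follows from the plan's own equations without simulation.

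**Hand arithmetic.** V = 180 mL/kg and the 15-min interval are the plan's. For a rise of 0.10 in f over one interval, the omitted amount is 180 × C × 0.10/15:

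| C (mg/mL) | Source of C | Omitted (mg/kg/min) |
|---|---|---|
| 0.90 | assumed, near fasting | 1.1 |
| 1.31 | 2-h glucose, AHI < 5 group, preliminary sleep data | 1.6 |
| 1.53 | 2-h glucose, AHI > 5 group, same table | 1.8 |

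**Simulation A: one worked case.** This is a one-pool model using the plan's V, infusion rate (0.03 mg/kg/min), 75 g load, 40 mg/kg oral tracer and 15-min samples. Assumed: 90 kg, basal endogenous Ra 2.0, 85% of the load absorbed. The plan's equation for total Ra recovers the simulated value within about 0.07 mg/kg/min, so the fault lies in the split. Rates are in mg/kg/min.

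| Interval midpoint (min) | Ra | f | Plan's Ra,ENDO | Omitted term | Ra,ENDO with term | True |
|---|---|---|---|---|---|---|
| 22.5 | 6.07 | 0.283 | 4.35 | 3.16 | 1.19 | 1.18 |
| 52.5 | 6.70 | 0.613 | 2.59 | 1.81 | 0.79 | 0.78 |
| 127.5 | 3.38 | 0.801 | 0.67 | 0.03 | 0.64 | 0.64 |
| 262.5 | 1.83 | 0.483 | 0.95 | −0.60 | 1.55 | 1.55 |

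At 22.5 min, for example, 6.07 − 6.07 × 0.283 = 4.35, and 4.35 − 3.16 = 1.19. The plan's formula shows endogenous output at about twice basal when it has really been suppressed to 1.18. Half of basal is first reached at about 112 min instead of about 37 min.

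Varying weight (70–120 kg), absorption, depth of suppression, clearance, one or two pools, and whether E_P is taken at the middle or end of the interval left 440 runs with glucose between 65 and 200 mg/dL. The omitted term gave a largest early excess of +1.1 to +4.0 and a largest late deficit of 0.3 to 0.8. Taking E_P at the end of the interval shrinks the early error but still leaves at least +1.1 at its largest.

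**Simulation B: effect on the IC50.** One pool. Assumed: weight 80/95/110 kg; basal Ra 1.5/2.0/2.5; 90% absorbed with time constants 45/60/75 min; insulin peak 150 or 300 at 60 min; true half-suppression insulin 50/70/90. Clearance was set so that 2-h glucose was 131 or 153 mg/dL. Of 324 combinations, 195 could meet this with glucose between 60 and 200 mg/dL.

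- Ra,ENDO error at 15–30 min: +1.5 to +3.7 (median +2.6). Largest understatement after 3 h: 0.5 to 0.8.
- IC50 at 50% of peak suppression (the definition under Statistical Plan for Method Development), read at first crossing (an assumed rule): too high by 51–99 units at insulin peak 150 and by 165–214 at peak 300.
- With equal true IC50, the apparent gap between the two insulin profiles grows from 18–24 to 116–152. A curve fitted to all intervals gives a gap of the opposite sign.
- Raw suppressed Ra is off by 0.06–0.48 (median 0.19), and percent suppression by about 4–30 points (median 10).

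**Two-pool check of the repair.** Agreement of the corrected formula with one-pool data proves little, because data and formula share a model. On two-pool data (95 kg, basal 2.0, assumed exchange rates 0.05 and 0.07 per min, 39 of 72 scenarios kept) the plan's error at 15–30 min is +1.6 to +3.3. With the term restored, the error in any interval is at most 0.22 (accessible volume 140 mL/kg) or 0.56 (180 mL/kg).

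**The case against.** The algebra is hard to dispute; the stronger objections concern its reach.

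- **Link to the primary outcome.** The plan says glucose Ra, never Ra,ENDO, when it defines the IC50. This stands as a limit. Total Ra includes the drink and rises after it, so endogenous Ra is the likely reading, but the consequence for the primary test is conditional.
- **The models.** The plan says its model will distinguish the two sources, and OMM\* might be fitted to total Ra, which is unaffected. The text does not say which Ra is fitted, there or in the absorption model. Contamination of these models is therefore possible, not shown. Neither description supplies the missing term.
- **IC50 sizes.** The first-crossing rule is not in the plan, which fits a curve to Ra, by default a cubic. With differently shaped assumed curves, reading from a cubic fit gave biases of about 24–92 (insulin peak 150) and 85–221 (peak 300), against 58–99 and 158–223 at first crossing. The size depends on the rule. The 18–24 gap found even with correct Ra also shows that the rule itself can create a difference.
- **Room for refinement.** These are proposed calculations, with an early data review and provision for refinements. Nothing there names this term, and smoothing the computed points does not restore it.

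**Conclusion.** The concern holds. The formula is wrong as written, and the sign of the error follows from the plan's own equations: Ra,ENDO is too high before the plasma oral-tracer peak and too low after it. In simulation A the peak falls at about 1.5 to 3 hours.

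The sizes rest on assumed absorption, insulin and clearance curves. Under those assumptions the early error is comparable with or larger than basal endogenous output, and the late error is smaller. If the primary IC50 uses Ra,ENDO, most of the simulated shifts exceed the plan's SD of 39 and its target difference of 35, although the lowest cubic-fit shift (24) does not. The IC50 and group-gap figures are illustrative, and the direction of any PCOS–control bias is not known. Peak-suppressed Ra and percent suppression are generally less exposed than the IC50, but an error of up to about 30 points in percent suppression is not negligible.

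This should be corrected before endogenous Ra is used in any analysis.

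**What to change.** For each sampling interval, replace the split with:

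`Ra,EXO = Ra × (mean E_P)/E_D + V × ((C1 + C2)/2) × ((E_P2 − E_P1)/(t2 − t1))/E_D`

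and keep Ra,ENDO = Ra − Ra,EXO. Alternatively, take Ra,EXO from a specified non-steady-state oral-tracer model. Residual error under two-pool kinetics should be acknowledged.

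The plan should also state:

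- that the primary IC50 is computed on Ra,ENDO;
- the rule for reading it: half of basal or half of peak suppression, and from raw intervals or a fitted curve;
- which Ra, total or split, is fitted in OMM\* and in the absorption model.

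The cost is one formula line, a few sentences and a re-run. The existing formula already needs E_P from the 15-min samples, and E_D is a single value for the drink, so no samples or visits are added. As a tidy-up, the list of tracer analyses under Visit 3 should name plasma 1-13C-glucose.
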